 - d. Total bilirubin above $1.5 \times$ upper limit of the normal range (ULN), except in patients with predominantly unconjugated hyperbilirubinemia (e.g., Gilbert's syndrome)
 - e. Aspartate or alanine aminotransferase (AST or ALT) $>2 \times$ ULN
 - f. Alkaline phosphatase $>2 \times$ ULN
 - g. Creatinine clearance <30 mL/min

8.2.4 Medication Exclusions:

26. Any prior use of ixazomib or other proteasome inhibitor
27. Any prior use of rituximab
28. Any prior use of cyclophosphamide
29. Suspected intolerance, allergy, or hypersensitivity to ixazomib or any of its excipients
30. Ongoing use or expected use of any of the following therapies:
 - a. Investigational drug within the 28 days before screening (an investigational drug is defined as any drug that has not been FDA approved for marketing)
 - b. Strong CYP3A inducers (e.g. rifampin, rifapentine, rifabutin, carbamazepine, enzalutamide, phenytoin, fosphenytoin, phenobarbital, St. John's wort)
 - c. Methotrexate
 - d. Leflunomide
 - e. Azathioprine
 - f. Sirolimus
 - g. Tacrolimus
 - h. Oral corticosteroids at a dose >10 mg/d prednisone equivalent
 - i. D-penicillamine
 - j. Minocycline
 - k. Interferon- γ

- i. Endothelin-1 receptor antagonists (e.g., bosentan, ambrisentan or macitentan)
- m. Phosphodiesterase inhibitors (for use other than erectile dysfunction or Raynaud's phenomenon)
- n. Riociguat
- o. Tumor necrosis factor- α (TNF- α) inhibitor drugs
- p. Tocilizumab
- q. Rituximab
- r. Abatacept
- s. Cyclosporine
- t. Cyclophosphamide
- u. Intravenous immunoglobulin (IVIG)
- v. Nintedanib

8.2.5 General Exclusion:

- 31. Unsuitable for enrollment or unlikely to comply with study requirements, as assessed by the investigator

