9.2 Ixazomib Dose Modification or Interruption

9.2.1 Management of Clinical Events

Adverse drug reactions such as thrombocytopenia, diarrhea, fatigue, nausea, vomiting, and rash have been associated with ixazomib treatment. Further details of management of ixazomib AEs are described in the ixazomib IB [143].

Ixazomib dose modification or interruption will be allowed for safety or tolerability reasons at any time during the study at the discretion of the investigator. In general, if dose modification is necessary, the first ixazomib dose reduction is to 3 mg; second dose reduction is to 2.3 mg; and thereafter, to discontinue use.

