 2. Upon recovery of the platelets $\geq 75,000/\text{mm}^3$ ixazomib administration may resume at the first reduction dose of 3 mg with weekly monitoring of CBC for the remainder of that study cycle until the next study visit. The 3 mg dose should follow the dose cycle schedule for the remainder of that study visit and subsequent study visits unless recurrent thrombocytopenia $\leq 30,000/\text{mm}^3$ occurs.
 3. In that instance, if thrombocytopenia is asymptomatic or associated with petechiae /bruising without other significant bleeding, ixazomib administration will be interrupted and paused until the platelet count is $\geq 50,000/\text{mm}^3$ upon retesting of the CBC daily and then weekly until the platelet count is $\geq 75,000/\text{mm}^3$.
 4. Upon recovery of the platelets $\geq 75,000/\text{mm}^3$, ixazomib administration may resume at the second reduction dose of 2.3 mg with weekly monitoring of CBC for the remainder of that study cycle until the next study visit. The 2.3 mg dose should follow the dose cycle schedule for the remainder of that study visit and subsequent study visits unless recurrent thrombocytopenia $\leq 30,000/\text{mm}^3$ occurs.
 5. In that instance, ixazomib administration will be discontinued. If thrombocytopenia is asymptomatic or associated with petechiae/ bruising without other significant bleeding, the thrombocytopenia will be monitored with a CBC daily until the platelet count is $\geq 50,000/\text{mm}^3$ and then weekly until the platelet count has returned to $\geq 75,000/\text{mm}^3$. The participant will be discontinued from the study and will proceed to complete assessments and procedures for early discontinuation (See 15.0 Early Discontinuation).

9.2.3 Non-Hematologic toxicity:

9.2.3.1 In the event of either new or worsening baseline peripheral neuropathy, ixazomib dose will be managed as follows:

- **If grade 1 (mild) new peripheral neuropathy with pain or worsening baseline peripheral neuropathy grade 2 (moderate):**
 1. Ixazomib administration will be interrupted and paused until the peripheral neuropathy is grade 1 or lower without pain, or at patient's baseline.
 2. If recovery of the neuropathy has occurred, ixazomib administration may resume at the first reduction dose of 3 mg and should follow the dosecycle schedule for the remainder of that study visit and subsequent study visits unless recurrent worsening neuropathy occurs.

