9.2.3.2 In the event of either new or worsening rash, ixazomib dose will be managed as follows:

- **If new grade 1 (mild) or 2 (moderate) rash for which there is no other immediate explanation** ixazomib dose will be managed as follows:
 1. Ixazomib administration will be interrupted and paused until the rash is grade improved grade 1 or resolved if grade 1.
 2. Upon improvement of the rash, ixazomib administration may resume at the first reduction dose of 3 mg and should follow the dose cycle schedule for the remainder of that study visit and subsequent study visits unless any recurrent or worsening of baseline rash occurs.

remainder of that study visit and subsequent study visits unless recurrent rash grade 2 occurs.

3. In that instance, ixazomib administration will be interrupted and paused until the rash is improved grade 1 or resolved if grade 1.
4. Upon improvement of the rash, ixazomib administration may resume at the second dose reduction dose of 2.3 mg and should follow the dose cycle schedule for the remainder of that study visit and subsequent study visits unless recurrent rash grade 2 occurs.
5. In that instance, ixazomib administration will be discontinued. The participant will be monitored until the rash is improved grade 1 or resolved. The participant will be discontinued from the study and will proceed to complete assessments and procedures for early discontinuation (See 15.0 Early Discontinuation).

- **If grade 3 (severe) rash for which there is no other immediate explanation** ixazomib dose will be managed as follows:

1. Ixazomib administration will be discontinued. The participant will be monitored until the rash is improved grade 1 or resolved. The participant will be discontinued from the study and will proceed to complete assessments and procedures for early discontinuation (See 15.0 Early Discontinuation).

9.2.3.3 In the event of hepatic impairment ixazomib dose will be managed as follows:

- If serum alkaline phosphatase is not more than 2 X upper limited of normal (ULN); total bilirubin is not greater than 1.5 X ULN except in patients with predominantly unconjugated hyperbilirubinemia (e.g., Gilbert's syndrome), and AST or ALT is not more than 2 X ULN, ixazomib dose will be managed as follows:

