 1. Ixazomib administration will be revised to the first reduction dose of 3 mg and should follow the dose cycle schedule for the remainder of that study visit with weekly monitoring of alkaline phosphatase, total and indirect bilirubin, and AST or ALT for the remainder of that study cycle until the next study visit. The 3 mg dose should follow the dose cycle schedule for the remainder of that study visit and subsequent study visits unless worsening of liver function tests is observed.
- If serum alkaline phosphatase is greater than 2 X upper limited of normal (ULN), total bilirubin is greater than 1.5 X ULN except in patients with predominantly unconjugated hyperbilirubinemia (e.g., Gilbert's syndrome), and AST or ALT is more than 2 X ULN, ixazomib dose will be managed as follows:
 1. Ixazomib administration will be discontinued. The participant will be monitored weekly until the liver function tests return to baseline or resolve. The participant will be discontinued from the study and will proceed to complete assessments and procedures for early discontinuation (See 15.0 Early Discontinuation).

9.2.3.4 If other nonhematologic adverse events, grade 2 or 3, ixazomib dose will be managed as follows:

1. Ixazomib administration will be interrupted and paused until the adverse event has improved to grade 1 or resolved.

2. Supportive care for the adverse event may be considered as clinically indicated.
3. Upon improvement of the adverse event to grade 1 or resolution, ixazomib administration may resume at the first reduction dose of 3 mg and should follow the dose cycle schedule for the remainder of that study visit and subsequent study visits unless a recurrent adverse event grade 2 or 3 of the same nature occurs.
4. In that instance, ixazomib administration will be interrupted and paused until the adverse event has improved to grade 1 or resolved.
5. Upon improvement of the adverse event to grade 1 or resolution, ixazomib administration may resume at the second reduction dose of 2.3 mg and should follow the dose cycle schedule for the remainder of that study visit and subsequent study visits unless a recurrent adverse event grade 2 or 3 of the same nature occurs.

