9.3 Restarting Ixazomib

Whether ixazomib can be restarted after a treatment interruption will depend on reason for the interruption; and if an adverse event (AE) its severity and its duration.

9.3.1 Interruption ≤28 Days:

- Ixazomib treatment can be restarted with dose modification as specified according to the type of adverse event. Dose up-titration back to ixazomib doses used during prior cycles associated with an adverse event will not be permitted.

9.3.2 Interruption >28 Days:

- **For an AE:** Treatment cannot be restarted after an interruption of >28 days because of a persisting AE. Ixazomib will be permanently discontinued, and the patient discontinued from the study and will proceed to complete assessments and procedures for early discontinuation (See 15.0 Early Discontinuation).
- **For Other Reasons:** If treatment is interrupted for >28 days for any other reason, ixazomib treatment can be restarted at the discretion of the investigator. If treatment is restarted, the ixazomib dose will be the most recent dose level being used prior to the interruption.

After restarting therapy, study visits will continue to be scheduled relative to Day 1 of study participation. The total study duration will be 28-29 weeks, starting with Day 1, and if dosing is interrupted, the study duration will remain unchanged.

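### First-event dose reductions in 9.2.2 and 9.2.3 name a fixed 3 mg whatever the current dose, so a new toxicity on 3 mg may bring no reduction, and for a participant on 2.3 mg the lower hepatic branch conflicts with 9.2.1 and 9.3.1

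*Combined protocol and SAP*

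**What the plan says.** Participants start on 4 mg on days 1, 8 and 15 of each 28-day cycle (9.1). Section 9.2.1 allows modification or interruption at the investigator's discretion and gives a general order: "the first ixazomib dose reduction is to 3 mg; second dose reduction is to 2.3 mg; and thereafter, to discontinue use". It does not say whether reductions are counted across toxicity types.

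The type-specific rules follow. Six sequences hold the drug and then allow it to restart at 3 mg: neutrophils (9.2.2.1), platelets (9.2.2.2), two for neuropathy (9.2.3.1), rash (9.2.3.2) and other nonhematologic events (9.2.3.4). The neutrophil and platelet sections share the wording "ixazomib administration may resume at the first reduction dose of 3 mg with weekly monitoring of CBC". In these six, 2.3 mg is reached only when the same toxicity recurs.

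The seventh is the lower hepatic branch of 9.2.3.3. It has no hold and uses *will*: "Ixazomib administration will be revised to the first reduction dose of 3 mg". It applies when alkaline phosphatase and bilirubin are within stated limits and "AST or ALT is not more than 2 X ULN, ixazomib dose will be managed as follows". Above the limits, the instruction is "Ixazomib administration will be discontinued. The participant will be monitored weekly until the liver function tests return to baseline or resolve".

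Section 9.3.1, headed for interruptions of 28 days or less, sends the restart dose back to the rule for that type of event and adds: "Dose up-titration back to ixazomib doses used during prior cycles associated with an adverse event will not be permitted".

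**The concern.** A reduction step is meant to lower exposure after a toxicity. A step that names a fixed dose does so only if the participant is on a higher dose when it is applied. The seven first-event steps therefore work as intended from 4 mg, but nothing limits them to participants on 4 mg.

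Safety and tolerability is the primary objective, and both the lab visits and the office visits (18.3, 25.2) tell staff to implement the modification designated in these sections. More than one type of toxicity in the same participant is foreseeable. Section 9.2.1 lists several drug reactions, and section 5.0 states that the safety profile of mycophenolate, taken by 6 of the 12 planned participants, overlaps with that of ixazomib for hematologic, gastrointestinal and liver effects. If staff read the steps differently, similar participants would receive different doses after similar events.

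**Working it through.** The protocol states no figure to reproduce. The check applies each first-event step to each possible current dose and compares the result with 9.2.1 and 9.3.1.

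**Inputs.** Dose levels 4, 3 and 2.3 mg and three doses per cycle (9.1, 9.2.1). First-event steps naming 3 mg: neutrophils 1 + platelets 1 + neuropathy 2 + rash 1 + lower hepatic 1 + other nonhematologic 1 = 7. Steps tied to the current dose: 0 of 7.

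**Dose changes** (new dose / current dose − 1):
- 4 to 3 mg: 3/4 − 1 = −25%
- 3 to 3 mg: 3/3 − 1 = 0%
- 3 to 2.3 mg: 2.3/3 − 1 = −23.3%
- 2.3 to 3 mg: 3/2.3 − 1 = +30.4%

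**Per full cycle:** 3 × 3 mg = 9.0 mg; 3 × 2.3 mg = 6.9 mg; difference 2.1 mg.

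**First event of a new type, by current dose:**

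| Current dose | Six hold-and-resume steps | Lower hepatic branch | 9.2.1 ladder, if counted across types |
|---|---|---|---|
| 4 mg | 3 mg (−25%) | 3 mg (−25%) | 3 mg |
| 3 mg, after another toxicity | 3 mg permitted (0%) | 3 mg named (0%) | 2.3 mg (−23.3%) |
| 2.3 mg | 3 mg named, but this is a restart and 9.3.1 normally bars it | 3 mg named (+30.4%), no restart involved | Discontinue |

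**The 3 mg row.** The ban in 9.3.1 does not help, because staying at 3 mg is not an increase. Only the general order in 9.2.1 points to 2.3 mg, and 9.2.3.4 points the other way by tying its next step to an event of the same nature.

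**The 2.3 mg row, hold-and-resume steps.** There is no real conflict. Sections 9.3.1 and 9.2.1 together point to not restarting.

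**The 2.3 mg row, lower hepatic branch.** Every written step down to 2.3 mg follows an interruption for an event on 3 mg, so 3 mg is normally a dose that 9.3.1 forbids returning to. But 9.3.1 is placed under restarts after an interruption, and this branch has none. One text names 3 mg and two point away from it, with no rule of precedence.

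**Screening limits.** The lower hepatic branch covers AST or ALT and alkaline phosphatase up to 2 × ULN and bilirubin up to 1.5 × ULN. These are the same limits that 8.2.3 sets for entry, so stopping a participant on 2.3 mg for such values would be stricter than the entry rule.

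**The case against.** The strongest case against is that the protocol, read as a whole, already leads to sensible doses. The six hold-and-resume steps say *may*, 9.2.1 gives 2.3 mg as the next level and leaves modification to the investigator, and the lab visits refer first to all of 9.2, including 9.2.1. The steps speak of a reduction dose, and an increase is not a reduction. A participant on 2.3 mg has normally had an event on 3 mg, so 9.3.1 shows that a return to 3 mg is not wanted. Holding the drug and resuming the same reduced dose after a mild event of a different type may even be deliberate.

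Most of this stands, and it limits the point. A reader might infer that the protocol directs a dose increase in a participant with a liver finding. The documents do not support that: 9.2.1 and 9.3.1 both point away from it, and what remains is a conflict with no stated precedence. A reader might also infer that the protocol requires an unreduced dose after a second type of toxicity. It does not, because 2.3 mg is open to the investigator throughout.

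These arguments do not supply the missing rule. Discretion allows 2.3 mg without naming it as the dose. The ladder in 9.2.1 is introduced only as a general order and is silent on counting across types. If the steps are read as covering only unreduced participants, no type-specific step covers a participant who is already reduced. The drafters tied a dose to the current level elsewhere: 9.3.2 restarts at the most recent dose after a long interruption for reasons other than an adverse event.

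**Conclusion.** The concern holds as a gap and a conflict in the dosing text. None of the seven first-event steps is tied to the current dose. On 3 mg, a first event of a different type permits an unchanged 9.0 mg per full cycle, where the 9.2.1 ladder counted across types would give 6.9 mg. On 2.3 mg, the lower hepatic branch names a dose 30.4% higher, against 9.2.1 and 9.3.1, and the protocol does not say which governs.

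Severity is minor to moderate. The study plans 12 participants, the documents give no frequency of mixed toxicities and none is assumed, and the hepatic conflict needs two earlier reductions plus liver values still within the entry limits. No sample size or error rate is affected. The conclusion concerns the protocol text only. Section 9.2.1 refers to the investigator's brochure for further management, and that was not available.

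**What to change.** Add to 9.2.1: *Reductions are counted across toxicity types. No step in 9.2 may raise the dose, with or without an interruption. Where a new event of a different type calls for the first reduction dose and the participant is already on 3 mg because of an earlier event, the dose is 2.3 mg.*

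Add to 9.2.3.3: *A participant already on 2.3 mg stays at 2.3 mg with the weekly liver tests; a participant placed on 3 mg by this branch stays at 3 mg unless liver tests worsen.*

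The restriction to a different type matters. Without it, a participant put on 3 mg by the lower hepatic branch, with stable values that still meet it, would be moved to 2.3 mg at the next check. Interruption-type events on 2.3 mg continue to follow 9.2.1: in general, discontinue, with investigator discretion kept. Discontinuation for liver values stays with the higher branch. State that the same rule applies in the extension, whose visits refer back to 9.2.

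The cost is a few sentences and brief retraining. No visits, tests or analyses are added, and the weekly liver tests are already specified in that branch. The downside is that some participants with mixed toxicities will receive a lower dose or stop earlier, and under 7.1 a permanent stop also ends study participation.

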10. History of a clinically significant environmental exposure that is known to cause pulmonary fibrosis including, but not limited to, drugs (e.g., amiodarone), asbestos, beryllium, radiation, or domestic birds or other exposures associated with hypersensitivity pneumonitis
11. Tobacco smoking within 3 months of screening or unwillingness to avoid smoking throughout the study (e.g., cigarette, pipe, or cigar)
12. History of unstable or deteriorating cardiac disease within the previous 6 months relative to study Day 1 including, but not limited to, the following:
 - a. Unstable angina pectoris
 - b. Myocardial infarction
 - c. Congestive heart failure requiring hospitalization
 - d. Uncontrolled clinically significant arrhythmia
 - e. Clinically significant pericardial effusion
 - f. Pulmonary hypertension (see 8.2.1 Exclusion Criteria - Disease Related)
13. Known underlying liver disease (e.g., hepatitis or cirrhosis)
14. Known or suspected peptic ulcer
15. Known active hematologic disorder other than anemia of chronic disease or iron deficiency anemia (hemoglobin < 8.0 gm/dl).
16. Known hematologic malignancy
17. History of any malignancy within the last 5 years other than non-melanoma skin cell cancers cured by local resection or carcinoma-in-situ
18. Prior stem cell or bone marrow transplant
19. Any condition that might be significantly exacerbated by the known side effects associated with ixazomib including known \geq grade 2 peripheral neuropathy
20. Pregnancy or lactation: Positive pregnancy test; currently lactating; or for women of childbearing potential and men, an unwillingness to maintain abstinence or highly effective contraception (see 8.1.3 Eligibility Criteria – Informed Consent and Protocol Adherence)

21. History of alcohol or substance abuse in the previous 2 years relative to study Day 1.
22. Expected to have study participation interrupted for a foreseeable medical or surgical event (e.g., organ, stem cell, or bone marrow transplant; orthopedic-related surgery).
23. Any condition that is likely to result in the death of the patient within 12 months.
24. History of known or active COVID19 infection.

8.2.3 Laboratory Exclusions:

25. Any of the following screening test criteria:
 - a. Hemoglobin \leq 8.0 gm/dl
 - b. Absolute neutrophil count \leq 1000
 - c. Platelet count \leq 75,000

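### The liver stopping rule in 9.2.3.3 joins its tests with 'and', so most over-limit combinations of liver tests get no action from that rule

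*Combined protocol and SAP*

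**What the plan says.** Section 9.2.3.3 of the protocol has two bullets for hepatic impairment.

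- **3 mg bullet.** It opens "If serum alkaline phosphatase is not more than 2 X upper limited of normal (ULN); total bilirubin is not greater than 1.5 X ULN", keeps an exception for predominantly unconjugated hyperbilirubinemia, and adds that AST or ALT must not exceed 2x ULN. The action is 3 mg with weekly liver tests for the rest of the cycle. The 3 mg dose then continues through "subsequent study visits unless worsening of liver function tests is observed".
- **Discontinue bullet.** It opens "If serum alkaline phosphatase is greater than 2 X upper limited of normal (ULN), total bilirubin is greater than 1.5 X ULN", keeps the same exception, and continues "and AST or ALT is more than 2 X ULN, ixazomib dose will be managed as follows". The action is permanent discontinuation with weekly tests until recovery.

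Section 8.2.3 uses the same three cut-offs at entry, but under "Any of the following screening test criteria", so one test over limit is enough to exclude.

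Section 9.2.1 allows modification or interruption at any time at the investigator's discretion, refers to the investigator's brochure for further detail, and gives a general ladder: "the first ixazomib dose reduction is to 3 mg; second dose reduction is to 2.3 mg; and thereafter, to discontinue use". Section 15.0 lists unacceptable toxicity and investigator discretion as reasons to discontinue. Section 9.2.3.4 gives a pause-and-step-down rule for other nonhematologic events of grade 2 or 3.

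**The concern.** The two bullets look intended to divide liver results into within limits and over limits. The 3 mg bullet correctly joins its tests with 'and', since being within limits means every test is within its limit. The opposite of that is at least one test over. The discontinue bullet keeps 'and', so it describes only the extreme case in which all three are over.

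The result is inverted. A liver event with every value within limits must go to 3 mg with weekly tests. Bilirubin and AST/ALT both over limit, with ALP within its limit, gets no reduction, hold, stop or weekly monitoring from this rule.

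Safety and tolerability is the primary objective (6.1). Section 5.0 names liver effects as an area where ixazomib and MMF toxicity overlap and says that the combination has not been studied. Section 9.2 is the stated guide at 14 scheduled dose decisions, and the week 2, 6 and 10 lab visits cite 9.2.3.3 by number. Section 24 also plans summaries of dose modifications and discontinuations by group. With 6 patients per group, one patient handled differently moves a group rate by 1/6, about 17 percentage points.

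**Working it through.** The plan states no figure here, so the check is to list the patterns and apply both bullets.

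**Count A: AST/ALT as one test.** Three tests, each over limit or not, give 2^3 = 8 patterns, of which 8 − 1 = 7 have at least one test over.

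| ALP >2x ULN | Bilirubin >1.5x ULN | AST/ALT >2x ULN | Action from 9.2.3.3 |
|---|---|---|---|
| no | no | no | 3 mg |
| yes | no | no | none |
| no | yes | no | none |
| no | no | yes | none |
| yes | yes | no | none |
| yes | no | yes | none |
| no | yes | yes | none |
| yes | yes | yes | discontinue |

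Uncovered: 7 − 1 = 6 of 7 (three with one test over, three with two).

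**Count B: AST and ALT separate, both bullets literal.** There are 2^4 = 16 patterns, and 16 − 1 = 15 are over limit.
- Discontinue: ALP and bilirubin over, with AST, ALT or both over: 3 patterns.
- 3 mg: ALP and bilirubin within limits and AST or ALT within its limit. Apart from the all-within pattern, this admits isolated AST and isolated ALT elevation: 2 patterns.
- Neither: 15 − 3 − 2 = 10 of 15.

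If the 3 mg bullet is read as requiring both enzymes within limits, the uncovered number is 15 − 3 = 12 of 15.

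**Gilbert-type patients (bilirubin not counted), AST/ALT as one test.** There are 2^2 = 4 patterns, 3 of them over limit. One leads to discontinuation and 2 of 3 are uncovered.

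**With 'any' in the over-limit branch and 'neither AST nor ALT' in the 3 mg branch.** The over-limit branch takes 7 of 7 (Count A), 15 of 15 (Count B) and 3 of 3 (Gilbert-type). No pattern is unassigned and none falls in both branches.

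**Dose decisions that refer to 9.2.** Weeks 2, 4, 6, 8, 10, 12, 16 and 20 give 8. Weeks 24, 28, 32, 36, 40 and 44 of the extension give 6. The total is 14.

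**Whether another rule fills the gap.** Sections 9.2.1 and 15.0 permit action but set no liver threshold. Section 9.2.3.4 covers *other* events, which arguably leaves liver events out, and it starts at grade 2. Section 21.2.1 grades severity mainly by discomfort and daily activities, which fits a symptom-free enzyme rise poorly. Section 23.1 names CTCAE for SAE reports, and 24.5 plans grade 3 and 4 laboratory listings without naming a scale.

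**The case against.** The strongest objection concerns the remedy. Section 8.2.3 is an entry criterion, not a stopping rule. Elsewhere 9.2 usually pauses and steps down first: neutrophils, platelets, grade 1 and 2 neuropathy and rash, and other grade 2 or 3 events. Making any single exceedance a permanent stop would be out of line with that. A patient enrolled at 1.9x ULN could be stopped at 2.1x on one unconfirmed value, although 21.1.1 discounts values that a repeat does not confirm. A stopped patient also loses the extension (25.1). This stands, and a reader should not infer from 8.2.3 that every isolated exceedance must end treatment.

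The second objection is that safeguards exist. Section 15.0 is a direct stop route, 9.2.1 allows an immediate hold, 19.0 allows extra tests, and 21.1.1 follows clinically significant values. The investigator's brochure may say more, but it is not available here. Twelve patients in one program also limit how far practice can vary. This stands as a limit on the consequence: the documents do not support reading the gap as the absence of any safeguard. It does not repair the rule, because these routes rest on judgment or set no liver threshold in the protocol text.

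The third is that 6 of 7 depends on treating AST/ALT as one test. This also stands, which is why both counts are shown. An isolated AST or ALT rise cannot be called uncovered on the literal reading, since the 3 mg bullet catches it. Bilirubin with AST/ALT, or two tests including ALP, is uncovered on either reading.

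**Conclusion.** The point holds. As written, 9.2.3.3 stops drug only when ALP, bilirubin and AST or ALT are all over limit, and it leaves 6 of 7 over-limit patterns (AST/ALT as one test) or 10 of 15 (separate tests, literal reading) with no action from that rule. Confidence is high, because the conclusion rests only on the wording.

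The counts weight all patterns equally. A reader might infer that most patients with abnormal liver tests would go unmanaged. The documents give no pattern frequencies, so that does not follow. The practical risk is a delayed or inconsistent response to a liver signal. It should be fixed at the next amendment.

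**What to change.** Reword 9.2.3.3 as follows.

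1. The over-limit branch applies when **any** of these is met: ALP >2x ULN, total bilirubin >1.5x ULN (Gilbert-type exception kept), AST >2x ULN, or ALT >2x ULN.
2. The 3 mg branch requires that **neither** AST nor ALT is above 2x ULN, with ALP and bilirubin within their limits.
3. On any exceedance, hold ixazomib at once, repeat the tests, and monitor ALP, bilirubin, AST and ALT weekly.
4. Discontinue if the exceedance is confirmed. For a confirmed exceedance of one test only, the sponsor may instead keep the hold until values are back within limits and resume at 3 mg on the 9.2.1 ladder, subject to the 28-day limit in 9.3.2.

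A small clean-up would also help: point from worsening at 3 mg to the 9.2.1 ladder if values stay within limits, and to the over-limit branch otherwise.

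The cost is amendment text. Naming both enzymes should need no extra draw beyond the weekly one, since both are in the serum chemistry panel (17.2.3). The downside is perhaps a few more holds or discontinuations; the documents give no basis for a number. A patient who stops loses extension eligibility (25.1), although post-discontinuation monitoring (15.1.1) remains available.
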